7.2. Independent Monitoring Committee (IMC)

Data monitoring and safety oversight is to be carried out via an independent monitoring committee (IMC) composed of at least three members beyond the principal study team. A clinician with experience in relevant disease research will chair the IMC and the other two members will be a statistician and a second clinician with human subject research monitoring expertise. An IMC is planned over a Data Safety Monitoring Board (DSMB) based on the National Institute of Health (NIH) and National Center for Complementary and Integrative Health (NCCIH) listed criteria with respect to data safety and monitoring. This study is single-site and phase I trial in scope. In addition, *Centella asiatica* is expected to be largely safe based on pre-clinical work and its long-standing position and extensive usage in herbal medicine. However, the use of blinded randomization and an elderly study cohort predicates the use of a multi-person committee and not just an independent monitor. See IMC charter.

7.3. Plan for review and reporting

The IMC will meet biannually to study un-blinded AE data coded by organ system, and on an ad-hoc basis as necessary, based on the cited reporting of severe AEs and continuing reviews to OHSU's IRB. Should it be determined that the protocol need to be amended as a result of data review, the principal investigator will submit a protocol amendment to the sponsor (NCCIH) for approval. Once approval is obtained from the sponsor, the amendment will be submitted to the OHSU IRB and monitoring body and the amendment approved prior to study amendment implementation, unless immediate implementation is required to protect the safety of the study participants. In such a case, the protocol amendment will be immediately implemented and the sponsor, OHSU IRB and IMC will be notified directly after protocol amendment implementation.

8. RISKS AND BENEFITS

8.1. Risks to subjects

Potential harm to participants will be minimized by excluding participants with the conditions detailed in section 4.3.2. The risks to the subjects participating in this proposed research project are mainly those associated with venous access, potential toxicity of the test material, and time commitment.

Venipuncture: The potential risks to participants are minimal and reversible. Likely risks include pain and bruising from the intravenous catheter or venipuncture needle insertion. Occasional risks include feeling lightheaded or faint during or immediately after a blood sample is collected. Unlikely risks include swelling, infection, transient hematomas, transient thrombophlebitis, a fractured catheter embolus, or an allergic reaction to the adhesives or sterilization materials used at the venous access point. To minimize risk, catheter insertions and blood draws will be conducted in a seated position and using aseptic technique by trained personnel.

Centella asiatica product: *Centella asiatica* is an edible plant. The Botanical Safety Handbook⁷⁸ classifies *Centella asiatica* as a Class 1 herb, i.e. one that can safely be consumed when used appropriately. The widespread use of *Centella* as a dietary supplement and human studies performed with *Centella asiatica*^{33-35,80,98,12} support its safety. At the doses given in this study, the risks are expected to be minimal and unlikely. The lowest dosage is based upon allometric scaling from mouse studies in which no toxicity was observed; however, the present product is a concentrated extract, and it is important to establish its safety, particularly in a vulnerable elderly population. We do not anticipate a great increase in adverse effects with the higher dosage, but are aware that they may occur. In particular, we anticipate potential transient gastrointestinal side effects such as nausea, gastric reflux/discomfort or diarrhea. Due to unknown interactions with pharmaceutical medications, we will exclude those on blood thinning medications (e.g. warfarin). We will also exclude those with hepatitis and/or liver disease, as there is potential for *C. asiatica* to harm the liver, and will closely monitor those on drugs with hepatotoxic potential (e.g., acetaminophen, methotrexate, pravastatin). *Centella asiatica* may cause sleepiness and drowsiness in large amounts, so individuals taking sedatives (besides occasionally for sleep) and Central Nervous System (CNS) depressants are likewise excluded, as the study drug could increase these side effects. Additional risks include allergic reaction to the intervention, which will be managed by oral or intravenous diphenhydramine depending on the severity.

Treatment-emergent suicidal ideation and behavior have been identified as a concern for a number of drugs and drug classes. Because of these concerns, a prospective assessment for suicidal ideation and behavior will be monitored. Heisel et al. (2011)¹³² have identified a “suicide ideation” subscale in the Geriatric Depression Scale (GDS). We are using the GDS as part of study procedures, and will pay special attention to the identified subscale questions to assess potential risk of suicidal ideation or behaviors.

Risks associated with a breach of confidentiality: There is a small risk that information about a study participant could be inadvertently disclosed to non-study personnel. Procedures to minimize this risk have been described in this protocol.

Other risks/discomforts associated with participation: The participants will experience a time burden by participation in the research study, as they will need to remain within the Clinical and Translational Research Center for 13 hours at each study visit (total 26 hours). Participants will be remunerated in a prorated fashion (\$40 per visit) for their participation. They will also be asked to follow a low plant diet, which may present an economic burden. To mitigate the burden associated with bringing food that conforms to the diet or purchasing food during their study visits, participants will be provided with three meals and snacks that conform to the diet for each study visit at no expense. As this study is being conducted only at the OHSU Marquam Hill campus, there are travel and parking expenses associated with study participation. To address this expense, participants will be provided with an option of a round trip taxi trip to their home (up to \$50) or a validated parking pass for each study visit at no expense.

8.2. Potential benefits to subjects

As this is a pilot pharmacokinetic study with single administrations of the intervention, it is unlikely participants will experience any direct benefits. The data on dosing and tolerability will be extrapolated to longer trials of CAP in patients with mild cognitive decline or Alzheimer’s disease.

9. DATA AND SPECIMENS

The principal investigator will oversee the management of the participants, intervention, and analysis, which will be carried out by the clinical investigators, research statistician, and research assistant. Data entry, quality control and preparation, and participant management will be ongoing throughout the study.

9.1. Data collection methods

Information will be collected from each participant and their representative by a study clinician and/or research assistant. These personnel will be blinded to the participant's dose. The procedures for obtaining research material will include a telephone screening form, a medical history form, cognitive screening questionnaires (Mini Mental State Examination and Clinical Dementia Rating), a mood-screening questionnaire (Geriatric-Depression Scale-15), a standardized adverse event questionnaire, a diet diary, electrocardiogram, urine collection and blood collection. The following will be recorded directly on the case report forms (CRFs) telephone screening form, a medical history form, cognitive screening questionnaires (Mini Mental State Examination and Clinical Dementia Rating), a mood-screening questionnaire (Geriatric-Depression Scale-15), and a standardized adverse event questionnaire. This data will then be input into the participant's instance of REDCap. Data will be collected directly from study participants specifically for research purposes. All blood collection will be performed at the CTRC. All data used for this project will be obtained only after receiving participant informed consent.

9.2. Handling of data and specimens

Upon enrollment, each participant will obtain a unique identification number. This number will be associated with all specimens and data collected from that participant. Following the collection of whole blood from the participant, a trained member of the study team will transfer the blood to the specified Vacutainer tubes. Vacutainers containing a 5 mL aliquot of blood for NRF2 analysis from the screening (6.6) and study visits (6.9) will be transferred to [name] laboratory for isolation of PBMC and measurement of gene expression and/or protein levels related to NRF2 activation (in collaboration with [name], OHSU). For analysis of CA compounds, study staff will process the blood by centrifugation in the CTRC's laboratory to separate the plasma for analysis. The isolated plasma will be transferred into labeled tubes and placed on ice until transported by a member of the study team via a sealed Styrofoam cooler labeled with biohazard to The Oregon Alzheimer Disease Center Biomarker Core Lab (Biomedical Research Building, OHSU). The plasma and a 50mL aliquot of the urine specimens will be stored in labeled boxes in [name] -70°C freezer for up to five years. All written data will be stored in a locked cabinet in [name] office (Richard Jones Hall, OHSU) for up to five years. All computerized data will be stored in OHSU's installment of REDCAP and in a password protected folder on the OHSU X-drive for up to five years.

9.3. Detection of *Centella asiatica* derived compounds in plasma and urine

Biological levels of *Centella asiatica* triterpenes, caffeoylquinic acids, and their metabolites will be assessed in both plasma and urine using high-performance liquid chromatography coupled to tandem mass spectrometry (HPLC-MS/MS). Plasma calibration curves will be made using pooled baseline human plasma from the study participants (one teaspoon (5 mL)/participant) separated by gender. The blank plasma will be spiked with increasing doses of commercially available reference triterpenes, caffeoylquinic acids and known metabolites, as well as appropriate internal standards (see below). If the blank plasma is found to contain traces of the analytes, we will calculate the true concentration by back extrapolation using the method of standard addition. A pooled baseline urine sample taken from participants (separated by gender) will be used as a "blank" urine sample for spiking with standards.

Triterpenes; Plasma (200 µl) and urine samples (3000 µl) will be mixed with phosphoric acid and internal standard (chrysin) before incubation with *E. coli* glucuronidase and *S. aerogene* sulfatase to release the analytes of interest from glucuronide and sulfate conjugates. Incubated samples are passed through a Supelco Supelclean™ C8 column, washed with dilute aqueous acetic acid to remove salts, and eluted with ammoniacal methanol. The eluant is vacuum dried, reconstituted in 200 µl of 1:1 methanol: ammonium acetate and filtered through a 0.2 µM spinfilter to remove residual particles before analysis. HPLC-MS/MS will be performed on an Applied Biosystems Q-Trap 4000 LC-MS instrument. The analytical method to be used is a modification of that described by Nair et al. (Nair, Menon et al. 2012) Chromatographic separation will be achieved using a Poroshell 120 EC18 column and methanol:ammonium acetate gradient. Triterpenes will be detected as their ammonium adducts with positive ion mode electrospray ionization using the following MS/MS transitions: AA (506/453) and MA (522/451), and chrysin will be detected as the molecular ion (255/255).

Caffeoylquinic acids and metabolites: Plasma (200 µl) and urine samples (3000 µl) will be mixed with ascorbic acid and isotopic internal standards (¹³C₉-caffeic acid, ¹³C₃-ferulic acid, and d₃-isoferulic acid) before incubation with *E. coli* glucuronidase and *S. aerogene* sulfatase to release the analytes of interest from glucuronide and sulfate conjugates. Incubated samples will be applied to a Phree® column along with acidified acetonitrile (1 mL) and passed through by centrifugation, precipitating proteins and removing lipids. The eluant will be vacuum dried, reconstituted in 200 µl of 66% aqueous acetonitrile with 0.66% formic acid and filtered through a 0.2µM spinfilter to remove residual particles. LC-MS/MS will be performed on an Applied Biosystems 5500 QTRAP HPLC-MS instrument. Chromatographic separation will be achieved using a C8 reversed-phase column and acidified acetonitrile:water gradient. Caffeoylquinic acids (CQAs), their metabolites and internal standards will be detected using negative ion mode electrospray ionization and the following MS/MS transitions: mono-CQAs (353/191); di-CQAs (515/353; 515/191); caffeic acid (179/135); ferulic acid and isoferulic acid (193/134); dihydrocaffeic acid (181/109); 4-methylcatechol (123/108); 4-ethylcatechol (137/122); ¹³C₉-caffeic acid (188/143); ¹³C₃-ferulic acid (196/136); d₃-isoferulic acid (196/134).

9.4. Analysis of total antioxidant compounds

Total antioxidant compounds in plasma will be measured at each time point using the OxiSelect™ kit (Cellbiolabs Inc.) and following the manufacturer's instructions. The assay, performed in 96-well plates, is a quantitative assay for measuring antioxidant potential within plasma samples. Following the reduction of ferric iron (Fe³⁺) to ferrous iron (Fe²⁺) by antioxidants in the sample, the kit colorimetric probe develops a blue color that is read at 540-600 nm. The antioxidant potential of samples is determined based on an iron standard curve and results are calculated at Fe²⁺ equivalents (µM) or FRAP value.

9.5. Investigation of blood biomarkers of NRF2 activation

These methods are described in Appendix 2.

9.6. Sharing of results with participants

All screening laboratory results, performed by the CLIA certified OHSU Core Laboratory, will be provided to the participant. If a screening result is found abnormal (an incidental finding), the participant will be instructed to share their result with their primary care provider. Electrocardiograms (EKGs) and comprehensive metabolic panels (CMPs) will be performed at each study visit. If the EKGs are found to be abnormal, the participant will be instructed to share their result with their primary care provider.

9.7. Data and specimen banking

All data obtained from this study will be used for research purposes only and will comply with HIPAA regulations. No genetic research will be performed on these specimens. The specimens and data collected relate specifically to this research project; however, plasma samples may be stored at -70°C in [name] laboratory for future analysis of newly identified bioactive compounds of *Centella asiatica*. No specimens will be sent to or used in a repository. All specimens will be labeled with each participant's unique numeric ID code but will not contain any identifiable participant information, and will be maintained at OHSU.

10. DATA ANALYSIS

10.1. Study outline

This is a phase 1 pilot clinical study using a blinded randomized crossover design. Participants will consume one of two single doses of CAP (2g or 4g) on two separate occasions at least 2 weeks apart. After each administration, blood and urine samples will be collected over a 10 hour period, and analyzed for compounds derived from CAP. The order in which the doses are administered will be randomized.

10.2. Reason for randomization

The order in which the doses are administered will be randomized so that some data will be available for both doses in case of dropouts after the first visit. It is also randomized to prevent a tolerance effect.

10.3. Justification of two-week washout

The minimum two-week period was chosen based on a balance between participant convenience (allowing sufficient time between the lengthy study visits), and the need to complete the study in a timely manner. An additional factor is that the compounds of interest, particularly the caffeoylquinic acids (CQAs), may also be derived from the diet. For this reason, participants will undertake a low phytochemical diet 48h before and during each study visit. As described below, we predict based upon the reported half-life ($t_{1/2}$) values of some compounds found in *Centella asiatica*, that 48h on the restricted diet will be sufficient to clear 97% of the starting levels of the compounds. We will compare baseline plasma levels of the compounds of interest prior to administration of each *Centella asiatica* dose (i.e. after 48h on low phytochemical diet and before CAP administration) to examine for sufficient washout between doses. The triterpenes (asiatic acid and madecassic acid, and their glycosides) will be most useful in this regard, as they have a narrower distribution in plants than the CQAs, and are less likely to be ingested from the general diet in the period intervening study visits.

10.4. Primary and secondary hypotheses

- The primary hypothesis is that the triterpene and caffeoylquinic acid components in CAP will be orally bioavailable, such that administration of CAP will result in elevations from baseline values of the plasma concentration of *Centella* triterpenes, caffeoylquinic acids (CQAs), and CQA metabolites, and that the magnitude of this elevation will be higher for the 4g dose of CAP than the 2g dose.
- A secondary hypothesis is that absorption of compounds from CAP will result in an increase in antioxidant potential of the plasma.
- An additional secondary hypothesis is that consumption of a single dose of CAP will be safe and well tolerated.
- An additional secondary hypothesis is that consumption of a single dose of CAP will result in activation of the NRF2 antioxidant pathway over a 6 hour period.

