1. STUDY OBJECTIVES

1.1. Purpose

The purpose of this study is to measure the oral bioavailability and pharmacokinetics of known bioactive compounds from a standardized *Centella asiatica* water extract product (CAP) in

mildly demented elders on cholinesterase inhibitor therapy. Compound levels will be measured in human plasma and urine over 10 hours after acute oral administration of two doses of the botanical extract product. The dose giving maximum plasma levels (C_{max}) closest to those observed in our mouse studies, the area under the curve (AUC_{0-10}), as well as the rate of clearance ($t_{1/2}$) of the known compounds and time of maximum concentration (t_{max}), will be identified. These data will be used to inform decisions on the dosage and dosing frequency for future clinical trials.

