10.5. Primary and secondary outcome measures

- Primary outcome:
 - A change in pharmacokinetic parameters (C_{max} and AUC_{0-10}) of plasma analytes after treatment with a product made from a water extract of *Centella asiatica* (CAP) with a detectable difference between doses (2g and 4g).
- Secondary outcome:
 - The time of maximum concentration (t_{max}) and half-life ($t_{1/2}$) of the known bioactive compounds and their metabolites to help determine dosage intervals
 - Temporal changes in ferric reducing ability of plasma (FRAP) as an indicator of antioxidant potential over time
 - Safety and tolerability of acute doses of CAP determined by participant interviews, biometrics, electrocardiography, laboratory assessments of liver and kidney function, vital signs and questionnaires
 - The levels of triterpenes, caffeoylquinic acids, and their metabolites in a pooled urine sample collected over 10 h after CAP administration
 - Activation of the NRF2 antioxidant response element pathway in peripheral blood mononuclear cells (PBMC) over 6 hours following CAP administration.

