10.6. Specimen analysis

Each CAP derived analyte will be identified by its retention time and characteristic mass spectral fragmentation pattern using selected reaction monitoring. The peak area ratio to the appropriate internal standard will be identified and evaluated against the standard calibration curve of each analyte. Each analyte's concentration will be used to generate a concentration-time curve for pharmacokinetic profiling. Pharmacokinetic (PK) profiling of the triterpenes, CQAs and their metabolites will use non-compartmental analysis (NCA) to calculate common PK parameters such as peak concentration (C_{max}), the time at peak concentration (t_{max}) and the total 10 hour bioavailability represented by the total area under the curve (AUC_{0-10}). These will be compared to the mouse data in order to assess appropriateness of dosing level. Other calculable NCA metrics will also be determined, such as the elimination half-life ($t_{1/2}$) calculated from the profile tails and the mean residency time (MRT) of the compounds in plasma. Descriptive assessment will be done at each of the doses to give basic PK summarization of the various CA compounds and total antioxidant compounds measured by FRAP. NRF2 antioxidant pathway related gene and/or protein levels will be compared in PBMCs from the screening visit, the baseline study visit sample and hourly up to 6h following CAP administration. Dose dependence of the study outcomes will be determined by evaluation of the within-subject differences in study outcomes between the 2g and 4g CAP doses.

Assumptions of normality will be confirmed using outcome density distributions alongside utility from formal tests, such as the Anderson-Shapiro. In instances of normality violation, statistical transformation such as natural logs and square roots will be considered as will non-parametric equivalent tests such as the paired Wilcoxon rank-sum test. Standard diagnostics will be very conservative given the limited number of available subjects but clearly obvious outliers will be removed as necessary. Non-continuous variables such as t_{max} will have frequency distributions compared between doses using chi-square testing. Although all CA compounds of interest and PK parameters are defined a priori, multiple comparison correction to p-values will be applied as necessary, with final two-tail significance defined at $p < 0.05$.

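### The primary hypothesis is a rise from baseline, but section 10.6 analyses uncorrected Cmax and total AUC0-10 and plans no test of the rise

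*Combined protocol and SAP*

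**What the plan says.** - **Hypothesis (section 10.4).** The primary hypothesis has two parts: "administration of CAP will result in elevations from baseline values of the plasma concentration" of triterpenes, CQAs and CQA metabolites, and this rise is greater at 4 g than at 2 g.
- **Outcome (section 10.5).** The primary outcome is "A change in pharmacokinetic parameters", namely Cmax and AUC0-10. It does not say what the change is measured from.
- **Analysis (section 10.6).** AUC0-10 is "the total 10 hour bioavailability represented by the total area under the curve". Within a dose, "Descriptive assessment will be done at each of the doses to give basic PK summarization". Between doses, "Dose dependence of the study outcomes will be determined by evaluation of the within-subject differences in study outcomes". On dose level, "These will be compared to the mouse data in order to assess appropriateness of dosing level"; section 1.1 looks for the dose whose peak levels are "closest to those observed in our mouse studies".
- **A contrast in the same section.** NRF2, which is not a primary endpoint, is compared across the screening visit, "the baseline study visit sample and hourly up to 6h following CAP administration".
- **Pre-dose plasma.** A sample is drawn before dosing at each visit (section 6.9). Its stated uses for plasma analytes are a check on the diet (6.9), pooled blank plasma for calibration (9.3) and a check on washout (10.3).

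**The concern.** Both parts of the primary hypothesis concern the elevation. The planned analysis concerns the level reached. The two coincide only if pre-dose levels are negligible. Section 10.3 says that the compounds, CQAs in particular, may also come from food, and section 9.3 provides for traces in blank plasma.

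Three consequences follow. The rise at each dose has no planned inference. A diet-derived level counts as exposure from CAP in the Cmax and AUC0-10 that are reported and compared between doses. The same level is added to the human Cmax that is set beside the mouse values to judge whether the dose is appropriate.

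**Working it through.** **1. The plan's own figures.** Section 10.8 gives critical t values of 2.57 (Cmax, 6 participants) and 2.45 (AUC, 7 participants). The two-sided 0.05 values are t(5 df) = 2.571 and t(6 df) = 2.447, so both reproduce. They belong to a paired comparison of two doses. Section 10.8 has no calculation for a rise from baseline.

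**2. What baseline does to the dose contrast.** Write observed exposure at dose d as Y_d = E_d + B_d, where E is net exposure from CAP and B is the baseline contribution at that visit.

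- Difference: Y_4 - Y_2 = (E_4 - E_2) + (B_4 - B_2). Dose order is randomised, so B_4 - B_2 has mean zero. The raw difference is unbiased, but its variance grows with visit-to-visit variation in B.
- Ratio: with E_2 = 1, E_4 = 2 and a common baseline b, the ratio is (2 + b)/(1 + b). That is 1.91, 1.67 and 1.50 for b = 0.1, 0.5 and 1, against 2.00 net.

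**3. Power for the dose contrast, 8 participants.** Every input here is an assumption, because the documents give no SDs and no human pre-dose levels. The true ratio is 2. Net exposure is lognormal, with CV 50% between and 30% within persons. Baseline is lognormal, with CV 50% between persons and 30, 50 or 100% between visits. The test is a paired t on differences at two-sided 0.05, with 20,000 simulated trials per cell. Subtraction uses a pre-dose sample with 15% assay error and a stable baseline. Results repeat to about one percentage point.

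| Baseline as % of net 2 g exposure | Raw difference (visit CV 30 / 50 / 100%) | After subtraction |
|---|---|---|
| 3% | 90-91% throughout | 90-91% |
| 10% | 91 / 91 / 89% | 90-91% |
| 25% | 90 / 88 / 81% | 90-91% |
| 50% | 87 / 81 / 65% | 89-90% |
| 100% | 76 / 61 / 40% | 84-86% |

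The mean raw difference was 0.99-1.00 in every cell (true value 1). With 7 completers, raw power is 58-80% at a 50% baseline and 34-67% at 100%; after subtraction it is 82-83% and 76-79%.

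**4. Which statistic can test the rise.** Suppose there is no absorption and the level is flat. The largest of 12 post-dose samples then exceeds one pre-dose sample with probability 12/13 = 92%, by noise alone. I simulated 8 participants at the protocol's sampling times, with 10-20% sample error and a one-sided nominal level of 2.5%:

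- Cmax minus pre-dose, tested against zero: false rejection in about 93% of trials when all participants share one baseline, and 85% when baselines differ between people with CV 50%.
- Net AUC0-10 (AUC0-10 minus 10 h x pre-dose level), tested against zero: about 2 to 2.5%.
- Net AUC0-10 with negative values set to zero: about 20 to 27%.

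The obvious comparison, a peak against the pre-dose level, would therefore appear to show bioavailability almost regardless of the truth. The choice of statistic should be fixed in advance.

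**The case against.** The strongest reply is that the randomised dose contrast already tests bioavailability. Order is randomised, participants and the LC-MS analyst are blinded to dose, excipients are equal at both doses (section 5.1), and the diet rules are the same at both visits. A higher level at 4 g points to CAP and not to food. A within-visit rise has no placebo period behind it and is the weaker inference. This stands. A reader might infer that bioavailability can only be judged by eye, or that the dose comparison is biased; the documents support neither.

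A reader might also infer that the plan ignores the pre-dose sample. It does not: the sample serves the diet, washout and calibration purposes above and is the natural time-zero point of each concentration curve. What is absent is a correction or a comparison. Standard addition in section 9.3 corrects the calibration; it does not remove a participant's own pre-dose level.

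The design also limits residual levels: a 48-hour low-plant diet, conforming meals, a 10-hour fast and a predicted 97% clearance. The mice were on a low phytochemical diet too (section 3.1), so the human-mouse comparison is partly matched. These points stand and may make the effect small. They do not settle it, because the 97% rests on half-lives of only some compounds and refers to an unstated starting level.

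Finally, this is a pilot. It nevertheless states a primary hypothesis and a two-tailed significance level, so the analysis should address that hypothesis.

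**Conclusion.** The mismatch is real and can be read directly from sections 10.4 and 10.6: the rise has no planned test, and the dose contrast is made on total exposure instead of the elevation. The 2 g versus 4 g difference remains a valid test of dose dependence.

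The size is unknown. The effect on that contrast is negligible if baseline is up to about 10% of net 2 g exposure. It becomes material, with raw power of 65-87% at 50% and 40-76% at 100%, only if residual levels are high and vary between visits. A reader might infer that dietary contamination is large, but nothing in the documents shows it. Mouse peaks are no guide to scale, since section 3.1 gives a range of 15 to 2350 ng/mL. Nor would one baseline share fit all analytes: section 2.4 reports human peaks within about 1 hour for mono-CQAs and at 5.5 to 8.5 hours for dihydro metabolites. For triterpenes, which section 10.3 regards as less likely to come from food, correction should change little. All power figures rest on the assumed variances.

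**What to change.** In section 10.6, for each analyte and visit:

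1. Define net AUC0-10 = AUC0-10 minus pre-dose concentration x 10 h, keeping negative values, and net Cmax = Cmax minus pre-dose concentration. Apply one rule to pre- and post-dose values below the lowest calibration point.
2. Test the rise at each dose on net AUC0-10 against zero (one-sample t or signed-rank). Alternatively, report it with a 95% confidence interval and state in section 10.4 that the rise is descriptive. Do not test net Cmax against zero.
3. Compare net values between doses within subject, with unadjusted values as a sensitivity analysis.
4. State whether the mouse Cmax values are net of baseline, and put human and mouse values on the same basis. Mice were killed at each time point (Figure 2), so subtraction there could use only a group mean; if none exists, compare unadjusted with unadjusted and note the mouse diet.

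In section 10.5, say what the change is measured from.

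**Cost.** Wording only; the sample is already drawn. Subtraction adds the error of one pre-dose sample, which costs almost nothing at low baseline in the table above. It also assumes a stable level over 10 hours, which cannot be checked without a placebo period. If dietary levels are still falling, it over-corrects, which is conservative for the rise. As an illustration, 97% cleared in 48 h implies a half-life of 48/log2(1/0.03) = 9.5 h and a mean level over 10 h of 0.71 of the pre-dose value. Subtraction would then remove 0.29 of the baseline area too much.
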